6.3 Visit 3 - Stimulation Follow-up (Day 6) and Unscheduled Visits

After 5 days of treatment with a dose of 150 IU (Day 6 of stimulation), the subject will return to the clinic for monitoring and adjustment of gonadotropin dose, as needed. A TVUS will be performed and serum hormone levels (E2, P4) will be collected and evaluated via the local laboratory. The start/stop dates, dosages, duration of treatment, and results of all ultrasounds and blood analyses

Date: 10 Dec 2015 E-Protocol Amendment-19588; Ver. 1.0 Supersedes: 28 October 2015 Page 32 of 69

obtained during the stimulation will be documented in the eCRF as well as concomitant medications and AEs.

Trial Code: 000205

Based on follicular response assessed by TVUS, dosing can be adjusted daily as needed by 75 IU per adjustment. However, the minimum daily total dose is 75 IU and the maximum total daily dose of study drug may not exceed 300 IU. Dosing with HP-hMG or Gonal-f[®] can continue for a maximum of 20 days.

When the lead follicle measures \geq 14 mm and/or serum E2 levels are \geq 300 pg/mL, the GnRH antagonist (ganirelix acetate) will be initiated at a daily dose of 0.25 mg and continued throughout the gonadotropin treatment period and the exact stimulation day of administration will be documented in the eCRF.

Subjects will be monitored per the center's standard practice during the stimulation dosing between Days 7 to 20 or until the stimulation phase is complete or study treatment is discontinued. Although these visits are not protocol-specific and can vary based on each centers standard of care, the results of the TVUS, E2 levels, P4 levels, concomitant medications, and AEs will be documented in the eCRF as unscheduled stimulation visits. The TVUS and blood results from the final day of stimulation (day of hCG trigger administration) will be documented in the eCRF and blood samples sent to the central laboratory. Since the final day of stimulation may not be known until the late afternoon or evening of the hCG trigger dose, an extra blood sample/tube will be collected and stored onsite for each day of stimulation monitoring to ensure the final day of stimulation is collected. Subjects will receive a single subcutaneous injection of Ovidrel (choriogonadotropin alfa, r-hCG) to induce final follicular maturation when ≥ 3 follicles of ≥ 17 mm are detected on TVUS.

The time between two Ganirelix® injections as well as the time between the last Ganirelix injection and the hCG injection should not exceed 30h.

- When injecting Ganirelix in the morning, treatment with Ganirelix should be continued throughout the gonadotropin treatment period including the day of triggering final follicular maturation.
- When injecting Ganirelix in the afternoon, the last Ganirelix injection should be given in the afternoon prior to the day of triggering final follicular maturation.

Important Note: coasting is prohibited. If the criteria for hCG administration is not met after 20 days of treatment (i.e., subject does not have ≥ 3 follicles ≥ 17 mm in size), the subject will be discontinued from study treatment. An EOT Visit will be scheduled or completed at this time and the information will be documented in the eCRF.

Subjects are to return the pens and empty, partially used, and unused vials/cartridges of the IMP to the site in order to monitor compliance. The coordinator or designee will reconcile and document the returned drug product in the drug accountability log.

Trial Code: 000205

Date: 10 Dec 2015

E-Protocol Amendment-19588; Ver. 1.0

Supersedes: 28 October 2015

Supersedes: 28 October 2015 Page 33 of 69

6.4 Visit 4 - Day Following Administration of Ovidrel®

The subject will return to the center (in the morning) the day following the Ovidrel[®] injection for P4 and E2 samples to be submitted to the central laboratory; serum hCG will be analyzed at the local lab. A TVUS will be performed. The date, time, and dosage of Ovidrel[®] will be recorded as well as study medication compliance. Adverse events and concomitant medications will be assessed and documented. Any symptoms of OHSS will be closely monitored.

The cycle will be cancelled in case of poor ovarian response (if the Investigator judges that ≥ 3 follicles of ≥ 17 mm cannot be reached after a minimum of 10 days of stimulation).

Subjects who have an excessive response to ovarian stimulation (>30 follicles of ≥12 mm and/or E2 ≥5000 pg/mL) will have the fresh transfer cancelled, and the hCG trigger will be replaced with a GnRH agonist trigger (4 mg leuprolide acetate). If leuprolide acetate is administered, a blood sample for LH will be collected and analyzed at the local lab. All resultant expanded blastocysts will be vitrified after trophectoderm biopsy, with no fresh blastocyst transfer in order to decrease the risk of OHSS. Following oocyte retrieval and blastocyst evaluation, an End of Trial (EOT) Visit will be scheduled or completed and the information will be documented in the eCRF.

In order to minimize the risk of empty follicle syndrome, the subject will return the morning after hCG trigger to draw serum hCG, E2, and P4 levels. If the hCG level is <50 IU/L and/or P4 is <3.5 ng/mL, then a booster/rescue second dose of hCG must be given on that day as soon as possible. If the subject received the GnRH agonist trigger, the bloods drawn will be LH, E2, and P4 levels. If, after the GnRH agonist trigger, the LH is <15 IU/L and/or the P4 <3.5 ng/mL, a rescue/booster dose of hCG (Ovidrel®) should be given as soon as possible. Delay of oocyte retrieval will be left to the clinician's discretion and will be based on the time at which the rescue dose was administered.

6.5 Visit 5 - Oocytes Retrieval/Insemination

A TVUS will be performed and oocytes retrieved roughly 36 hours after hCG administration. Oocytes will be inseminated using partner or donor sperm by ICSI 4±1 hours after retrieval.

Oocyte maturity will be assessed at the time of ICSI. Fertilization (number of pronuclei) will be checked on Day 1 following oocyte retrieval. Embryos must be cultured individually in separate dishes/droplets following the Day 1 assessment. Embryo quality will be assessed on Days 3 and 5 following oocyte retrieval; in the case of late blasulation, assessment will be performed on Day 6 or Day 7, as needed. A standardized embryo grading system will be used and documented in the eCRF. Adverse events and concomitant medications will be assessed and documented.

Each subject will be provided with vaginal progesterone inserts (200 mg/day – ENDOMETRIN[®]) to begin luteal support on the evening of the day after oocyte retrieval. The dose will be administered following the instructions provided in the package insert. Luteal phase support will continue until negative β -hCG (10-14 days after blastocyst transfer) or 8-9 weeks gestation, if pregnant.

Date: 10 Dec 2015 E-Protocol Amendment-19588; Ver. 1.0 Supersedes: 28 October 2015 Page 34 of 69

6.6 Visit 6 - Blastocyst Transfer

On Day 5 following ICSI, a single blastocyst of the best quality available will be transferred; all remaining blastocysts will be frozen using the vitrification method. A transabdominal pelvic ultrasound or transvaginal ultrasound will be performed to assess the endometrial thickness and echogenicity pattern. Laser-assisted trophectoderm biopsy for preimplantation genetic screening (PGS) will be done on Day 5; in the case of late blasulation, biopsy will be performed on Day 6 or Day 7, as needed. All expanded blastocysts with Blastocyst Expansion and Hatching Status 3-6, Inner Cell Mass grading A or B, and Trophoectoderm Grading A, B, or C. (Gardner & Schoolcraft, 1999) should be biopsied. The results of the PGS will not be available prior to the fresh blastocyst transfer, but can be used for subsequent frozen blastocyst transfer cycles, if needed. Adverse events and concomitant medications will be assessed and documented.

Trial Code: 000205

The residual cells obtained from ART (including granulosa cells, immature eggs, eggs that do not fertilize, sperm that is left over after fertilization, or embryos that stop developing, developed abnormally, are aneuploid or that would be discarded after other embryos are selected for embryo transfer or freezing) may be considered for use for further research in a future sub-study. Some of the research may be genetic and/or may be used for some of the following reasons.

- To further our understanding of how patients' genetics affect the response to medications designed for ovarian stimulation.
- To develop new techniques to optimize our understanding of genetic and chromosomal regulation in eggs, sperm, and embryos.
- To improve embryonic efficiency by assessing genes, DNA, RNA, proteins, chromosomes and cellular pathologies.
- To characterize normal and abnormal expression of genes and their functions, as well as downstream effects of transcription and translation.
- To determine the frequency of embryo mosaicism and chromosomal irregularities (inversions, translocations, deletions, etc.)
- To study proteins and their structure, functions, and interactions.

Subjects who wish to participate in such a sub-study will be asked to consent to the donation of this material.

6.7 Visits 7, 8, and 9 - Pregnancy Monitoring

- Visit 7: All subjects will be required to return to the clinic approximately 10-14 days after blastocyst transfer for β-hCG assessment. If the first serum β-hCG is positive, a second confirmatory test will be performed approximately 2 days later. If the pregnancy test is negative, ENDOMETRIN[®] will be discontinued and EOT procedures completed. If conflicting results are obtained in the first 2 tests, a third test will be performed 2 days after the second test. If a positive β-hCG is confirmed, ENDOMETRIN [®] will continue up to 10 weeks from the time it was initiated until the EOT Visit.
- **Visit 8**: Subjects who are pregnant will return to the clinic 4-5 weeks after blastocyst transfer for clinical pregnancy assessment (TVUS showing at least 1 intrauterine gestational sac with fetal heartbeat).

Trial Code: 000205

Date: 10 Dec 2015

E-Protocol Amendment-19588; Ver. 1.0

Supersedes: 28 October 2015

Page 35 of 69

• **Visit 9:** Subjects with clinical pregnancy will return to the clinic 8-9 weeks after blastocyst transfer for assessment of ongoing pregnancy (presence of at least 1 intrauterine pregnancy with a viable fetus with a detectable fetal heartbeat).

An End of Trial (EOT) Visit will be scheduled or completed for non-pregnant subjects and the information will be documented in the eCRF.

Non-pregnant subjects: Subjects without 2 positive β -hCG tests, clinical pregnancy, or ongoing pregnancy in the fresh cycle, may undergo a single frozen blastocyst transfer within 6 months of each subject's date of randomization. The PGS results can be used to select the euploid blastocyst for frozen transfer. Frozen-thawed blastocyst transfer cycle data will be collected, including blastocyst transfer information (endometrial thickness and echogenicity, grade of blastocyst, ploidy of blastocyst, presence of blood, or mucus within catheter tip), β -hCG serum results, clinical pregnancy, and ongoing pregnancy for the first frozen blastocyst transfer cycle following negative pregnancy.

Subjects may also return to the study center for regularly scheduled clinic visits as required per study center standard of care. The data collected during these visits will not be documented in the eCRF unless it is new or is a change in concomitant medications, pregnancy, or AEs.

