Positive β -hCG will be confirmed by 2 positive β -hCG tests, the first performed approximately 10-14 days after blastocyst transfer with a second positive test 2 days later. Clinical pregnancy will be confirmed by TVUS, indicating at least 1 intrauterine gestational sac with fetal heart beat at 6-7

Date: 10 Dec 2015 E-Protocol Amendment-19588; Ver. 1.0 Supersedes: 28 October 2015 Page 19 of 69

weeks gestation (4-5 weeks after blastocyst transfer). Ongoing pregnancy will be confirmed by at least 1 intrauterine viable fetus at 10-11 weeks gestation (8-9 weeks after blastocyst transfer).

Trial Code: 000205

For subjects with no ongoing pregnancy in the fresh cycle or for those receiving agonist trigger, single frozen blastocyst transfer cycles can be initiated within 6 months of a subject's initial date of randomization. Single blastocyst transfer is mandatory. The PGS results can be used to select a euploid blastocyst for frozen blastocyst transfer. Frozen-thawed blastocyst transfer cycle data will be collected, including blastocyst transfer information (to include embryo grade, euploid status, endometrial thickness, presence of blood/mucus on transfer catheter tip, and whether blastocyst is retained in the catheter requiring a second pass), β -hCG test results, clinical pregnancy, ongoing pregnancy, and live birth.

In women undergoing COS, an excessive response to follicular-stimulating agents may lead to the development of OHSS, which represents a spectrum that can be categorized as mild, moderate, or severe. Subjects who have an excessive response to ovarian stimulation (>30 follicles that are \geq 12 mm each and/or serum E2 \geq 5000 pg/mL) will have the cycle cancelled and converted to freeze all with GnRH agonist trigger. That is, the subject will receive 4 mg of leuprolide acetate administered subcutaneously at least 12 hours after the last dose of the GnRH antagonist; TVUS-guided oocyte retrieval will be performed approximately 36 hours later, and all resultant blastocysts will be vitrified after trophectoderm biopsy, with no fresh blastocyst transfer, to decrease the risk of OHSS.

All cases of OHSS will be considered AEs and will be recorded in the source documents for that subject and on the AE page in the eCRF. Severe OHSS that requires medical or surgical intervention (i.e., paracentesis, hospitalization) is considered a serious adverse event (SAE). See Section 7.1.6 for definitions of mild, moderate, and severe OHSS.

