Post-trial follow-up extends to collection of delivery information (live birth and neonatal health to include APGAR scores, birth weight, gestational age at birth, presence of congenital anomaly/birth defect, and cause of neonatal death, if applicable), which will be collected for all subjects with an ongoing pregnancy in the fresh cycle or the 6-month post-randomization frozen-thawed blastocyst transfer cycles. Live birth rate after the fresh cycle and cumulative live birth rate after fresh and 6-month post-randomization frozen-thawed blastocyst transfer cycles will be evaluated as part of the post-trial follow-up.

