6.9 Pregnancy Follow-Up

After confirmation of ongoing pregnancy in the fresh cycle or the 6-month post-treatment frozen-thawed blastocyst transfer cycle, the site will be required to collect delivery information (live birth and neonatal health). The follow-up will be conducted by the study center via telephone or mail and recorded in the eCRF. The site will also document miscarriage/pregnancy loss (spontaneous and/or induced), date of live birth, number of deliveries, gestational age at delivery, birth weight at deliveries, gender, and congenital anomalies/birth defects. Live birth rate after the fresh cycle and

Trial Code: 000205

Date: 10 Dec 2015

E-Protocol Amendment-19588; Ver. 1.0

Supersedes: 28 October 2015

Page 36 of 69

cumulative live birth rate after fresh and 6-month post-treatment frozen-thawed transfer cycles will be evaluated as part of the pregnancy follow-up.

Date: 10 Dec 2015 E-Protocol Amendment-19588; Ver. 1.0 Supersedes: 28 October 2015 Page 37 of 69

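### Protocol 6.7 records a narrower set of frozen cycles than 3.1.2 and 3.3.7, so cumulative live birth could be under-recorded, including in freeze-all subjects

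*Protocol*

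**What the plan says.** Protocol 6.7, on subjects who are not pregnant after the fresh cycle, says they "may undergo a single frozen blastocyst transfer within 6 months of each subject's date of randomization". It then lists the frozen-cycle data: transfer details, β-hCG, clinical pregnancy and ongoing pregnancy, "for the first frozen blastocyst transfer cycle following negative pregnancy". Live birth is not in this list.

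Protocol 3.1.2 covers women whose fresh cycle did not lead to an ongoing pregnancy, and its sentence goes on to add a second group: "or for those receiving agonist trigger, single frozen blastocyst transfer cycles can be initiated within 6 months of a subject's initial date of randomization". Its data list ends with "clinical pregnancy, ongoing pregnancy, and live birth" and has no first-cycle limit. Its follow-up paragraph says the "cumulative live birth rate after fresh and 6-month post-randomization frozen-thawed blastocyst transfer cycles will be evaluated".

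Protocol 3.3.7 also writes of frozen transfers in the plural. It plans delivery follow-up of every ongoing pregnancy from the fresh cycle or the 6-month frozen cycles.

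Protocol 6.9 starts delivery follow-up "After confirmation of ongoing pregnancy in the fresh cycle or the 6-month post-treatment frozen-thawed blastocyst transfer cycle". That is one cycle, and the window is anchored to treatment instead of randomization.

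The endpoint itself (Protocol 2.2 and 9.6.4; SAP 9.4) is the proportion of subjects with at least one live birth over fresh and frozen transfer. None of these places says how many frozen cycles count. Details are left to a separate post-trial SAP, which is not among the documents.

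**The concern.** Section 6 gives sites their procedures. Table 1 has no frozen-cycle column, so 6.7 is the only place in Section 6 that itemizes frozen-transfer data. Where it is narrower than the design section, the narrower rule may be the one followed.

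Two groups are exposed. The first is subjects with a second or later frozen cycle inside the window. The second is freeze-all subjects. Under 6.4 they have no fresh transfer, and their end-of-trial visit follows retrieval and blastocyst evaluation, so they never reach the Visit 7 test. The condition of a preceding negative pregnancy does not describe them. In a population selected for AMH of at least 5 ng/mL, with conversion to freeze-all on excessive response, such subjects are foreseeable.

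Live birth is a stated secondary objective (2.1), and cumulative live birth is the first post-trial endpoint listed. A later analysis plan cannot restore outcomes that were never entered. If freeze-all rates differ between arms, the omission would also distort the comparison.

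**Working it through.** **1. The sections side by side**

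| Question | 6.7 | 3.1.2 | 3.3.7 | 6.9 |
|---|---|---|---|---|
| How many frozen cycles? | data for the first only | plural | plural | singular in one sentence, plural in another |
| Freeze-all subjects named? | no; the closing condition does not fit them | yes | no | no |
| Live birth recorded? | not listed | listed | through delivery follow-up | through delivery follow-up |
| Window runs from | randomization | randomization | randomization | treatment |

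The permission in 6.7 for a single frozen blastocyst transfer can mean one transfer, or one blastocyst per transfer. The statement in 3.1.2 that single-blastocyst transfer is mandatory, and inclusion criterion 6 (one blastocyst per cycle), fit the second meaning. On the first meaning 6.7 agrees with itself but conflicts with the plurals in 3.1.2 and 3.3.7.

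Gonadotropin dosing may last up to 20 days. If treatment in 6.9 means gonadotropin treatment, the two windows can therefore end up to about 20 days apart.

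**2. The plan's own figure**

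The cumulative endpoint has none. The primary sample size reproduces: (1.960 + 0.842)² × (0.25 + 0.25) / 0.12² ≈ 273 per arm against 275 stated, and 275 / 0.92 ≈ 299 per arm, or 598 against about 600. It concerns the fresh cycle only, so this point does not touch it.

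**3. Possible size (illustration only)**

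Every input is an assumption, given as low / middle / high:

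- live birth after fresh transfer: 50% throughout
- freeze-all share f: 5 / 15 / 25%
- uptake of a first frozen transfer u: 60 / 75 / 90%
- live birth per frozen transfer s: 40 / 50 / 60%
- second frozen transfer in the window after a failed first, v: 10 / 30 / 50%

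Subjects without a fresh-cycle live birth make up 0.5(1 − f) + f = (1 + f)/2 of the arm.

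A. Second-cycle births missed = u · s · (1 − s) · v · (1 + f)/2:

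- low: 0.6 × 0.4 × 0.6 × 0.1 × 0.525 = 0.0076
- middle: 0.75 × 0.5 × 0.5 × 0.3 × 0.575 = 0.0323
- high: 0.9 × 0.6 × 0.4 × 0.5 × 0.625 = 0.0675

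B. First-cycle births missed if freeze-all subjects are also left out = f · u · s:

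- low: 0.05 × 0.6 × 0.4 = 0.0120
- middle: 0.15 × 0.75 × 0.5 = 0.0563
- high: 0.25 × 0.9 × 0.6 = 0.1350

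| Points lost (births per 300) | Low | Middle | High |
|---|---|---|---|
| A: later cycles only | 0.8 (2) | 3.2 (10) | 6.8 (20) |
| A + B: freeze-all also left out | 2.0 (6) | 8.9 (27) | 20.3 (61) |

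**4. Possible effect on the treatment difference**

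If the freeze-all share differs between arms by d and first frozen cycles of these subjects are not recorded, the difference shifts by d · u · s. For d = 2 points at the low values this is 0.02 × 0.6 × 0.4 = 0.5 points. For d = 10 points at the high values it is 0.10 × 0.9 × 0.6 = 5.4 points.

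**The case against.** The best reply is that the wider rule is already in the protocol. Section 3.1.2 names agonist-trigger subjects just before its data list and carries that list through to live birth. Sections 3.1.2 and 3.3.7 plan delivery follow-up of every ongoing pregnancy in the 6-month frozen cycles, and 6.9 requires sites to record delivery outcomes. The opening condition of 6.7, no ongoing pregnancy in the fresh cycle, can itself take in freeze-all subjects. If only one frozen transfer is meant, the first-cycle limit loses nothing for subjects who had a fresh transfer.

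This stands as far as it goes, and it rules out three stronger readings:

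- A reader might infer that cumulative live birth cannot be measured. The sections just named provide for wider collection, and the endpoint definition does not say that all frozen cycles count.
- A reader might infer that sites are told not to enter later cycles. No section says so. The one non-entry rule, at the end of 6.7, concerns standard-of-care visits and still calls for a change in pregnancy to be recorded.
- A reader might infer a bias of known size in favour of MENOPUR from the background figures of 32% versus 49% high response. Those count women with at least 15 oocytes, which is not the freeze-all criterion, and no frozen-transfer rates are given.

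What the reply does not remove is the conflict. Under 6.7 the recorded set is narrower, and nothing says which section governs.

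**Conclusion.** The protocol contradicts itself on which frozen cycles are recorded and does not define how many count toward cumulative live birth. Sites following 6.7 alone could under-record the endpoint for later frozen cycles, if these occur, and for freeze-all subjects.

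The omission of live birth from the list in 6.7 is a lesser matter, since 6.9 picks up deliveries after an ongoing pregnancy.

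The size and direction of any bias are unknown. The ranges above show only what complete non-recording would do under assumed rates; they are not an estimate for this trial. Any bias in the comparison depends on freeze-all or frozen-transfer rates differing by arm.

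The consequence is confined to post-trial endpoints that are summarized descriptively. The eCRF and the post-trial SAP are not available, so what is captured in practice cannot be judged.

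**What to change.** Reconcile 6.7 with 3.1.2 and 3.3.7, for example: *Transfer, pregnancy and live birth data will be recorded for each frozen blastocyst transfer cycle initiated within 6 months of randomization, including in subjects who had an agonist trigger and no fresh transfer.*

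Also:

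- Reconcile the permission in 6.7 for a single frozen transfer with the plurals in 3.1.2 and 3.3.7. How many transfers are allowed is for the sponsor to state; this review takes no position on it.
- Change the post-treatment anchor in 6.9 to post-randomization.
- State in the endpoint definition (Protocol 2.2 and 9.6.4, SAP 9.4 and the separate post-trial SAP) which frozen cycles count.

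The cost is protocol wording, repeatable eCRF pages for frozen cycles, and some extra data entry at sites.

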7.1.3 Transvaginal Ultrasounds

Transvaginal ultrasounds (including ovaries, adnexa, endometrial thickness in mm, follicular development - diameter of each follicle in mm, hyper- or hypo-echogenicity will be documented and recorded in the eCRF), and if pregnant, presence of intrauterine gestational sac, fetal pole, and/or fetal heartbeat, will be collected. Other ultrasounds may be performed throughout the ICSI treatment per standard practice but will not be documented in the eCRF.

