9.1 Determination of Sample Size

The study has at least 80% power, with 275 subjects per treatment group, to demonstrate the non-inferiority of MENOPUR® to Gonal-f® in the ongoing clinical pregnancy rate at the 1-sided significance level of 0.025 with a 12% non-inferiority margin, by assuming an ongoing pregnancy rate of 50% for both treatment groups (Yeh et al. 2014). Assuming that 8% of the subjects may not be eligible for the PP analysis set, approximately 600 subjects will be randomized (1:1) into this study.

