STATISTICAL ANALYSIS PLAN

A Randomized, Assessor-blind Trial Comparing MENOPUR® (menotropins for injection) and Recombinant FSH (Follicle Stimulating Hormone) in a GnRH Antagonist Cycle with Single-Blastocyst Transfer in a High Responder Subject Population

000205

Investigational Product:	MENOPUR® (menotropins for injection)
Indication:	Development of multiple follicles and pregnancy in ovulatory women as part of an Assisted Reproductive Technology (ART) Cycle with ICSI
Phase:	4
Author:	[name]
Date of issue:	March 8, 2017
Version:	4.0

The information in this document is confidential and is proprietary to Ferring Pharmaceuticals A/S or another company within the Ferring Group. It is understood that information in this document shall not be disclosed to any third party, in any form, without prior written consent of an authorised officer of Ferring Pharmaceuticals A/S or another company within the Ferring Group

Change log

Version No.	Effective Date	Reason for the Change / Revision	Supersedes

2.0	21SEP2015	SAP based on Protocol dated 22JUL2015	Version 1
3.0	16Feb2017	
For some baseline characteristics the analysis based on the safety population has been removed. The summaries based on the mITT and PP populations were considered to be sufficient.For the primary analysis, the sensitivity analysis based on ITT population was removed. Furthermore, sub-group analysis by genetic testing was added.Clarification on protocol deviation analysis.Added forest plots and boxplots.Removed the logistic regression.Other minor clarification and corrections were made.	Version 2
4.0		
In the conduct of the study, it was observed that there were a number of patients that had their primary endpoint visit too early (up to 4 weeks early). Initially, it was planned to use the visit assessment for this analysis however, because of this observation visit windows were considered to be a more accurate assessment for the endpoint. In Section 9, the visit window has now been defined. Furthermore, if a patient has pregnancy assessment beyond this visit she will also be considered as responder.
 
To make it consistent, this type of window was also applied to the clinical pregnancy endpoint.
	Version 3

Author, Reviewers, and Approver of the Statistical Analysis Plan

Author: [name].
Senior Project Statistician, Biometrics
Ferring International Pharmascience Center US, Inc.

Reviewers: [name].
Vice President, Reproductive Health & Urology

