$\hat{\pi}_{Gonal-f}$: is the observed ongoing pregnancy rate of subjects randomized to Gonal-f® in a single fresh treatment cycle following a GnRH antagonist protocol.

$N_{MENOPUR}$: is the number of subjects randomized to MENOPUR®.

$N_{Gonal-f}$: is the number of subjects randomized to Gonal-f®.

$Z_{(1-\alpha/2)}$: is the 1- $\alpha/2$ percentile in the standard normal distribution.

α : is the significance level, i.e., 0.05.

Subjects who do not have at least 1 intrauterine pregnancy with a detectable fetal heartbeat at 10–11 weeks gestation (8-9 weeks after blastocyst transfer in the fresh cycle) due to missing data, early withdrawal, or any other reason will be considered treatment failures (i.e., not having ongoing pregnancy) unless they have an assessment of detectable fetal heartbeat at a later date. Hence, for the analysis of this endpoint all positive (detectable fetal heartbeat) ultrasound assessments that occur in the interval from the end of 7th week from fresh transfer till the end of study will be considered as responder for the primary endpoint (i.e., ultrasound assessment date – fresh transfer date + 1 \geq 7 *7 = 49). Forty nine days was used because the 8-9 weeks visit window included 50

(beginning of the 8th week) to 63 days after fresh transfer. The primary endpoint analysis will be based on the mITT analysis set.

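### SAP 9.2 fails a woman scanned before day 49 unless a later heartbeat ultrasound is on record, and the protocol does not make sure that such a scan is recorded, so some continuing pregnancies can count as primary failures

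*Protocol*

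**What the plan says.** **The scoring rule.** SAP 9.2 treats a woman without a heartbeat in the 8-9 week window as a failure "unless they have an assessment of detectable fetal heartbeat at a later date". It then makes this operational: any positive heartbeat ultrasound counts if assessment date minus fresh-transfer date, plus 1, is at least 49, up to the end of study. The version 4.0 entry in the SAP change log gives the reason: "there were a number of patients that had their primary endpoint visit too early (up to 4 weeks early".

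**Other wordings of the rescue.** The change log and SAP 9.1.3 speak of a later pregnancy assessment without limiting it to ultrasound. SAP section 12 speaks of a positive pregnancy test after the 8-9 week window.

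**What is recorded after Visit 9.** Protocol 8.3 makes the visit at about 8-9 weeks the final study visit for a pregnant subject, and Table 1 lists no ultrasound after it. Protocol 6.7 allows further standard-of-care visits but says that their data "will not be documented in the eCRF unless it is new or is a change in concomitant medications, pregnancy, or AEs". Protocol 7.1.3 adds: "Other ultrasounds may be performed throughout the ICSI treatment per standard practice but will not be documented in the eCRF". Under Protocol 6.9, once ongoing pregnancy is confirmed, "the site will be required to collect delivery information (live birth and neonatal health". SAP 9.2 makes no use of that delivery information.

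**The concern.** Version 4.0 replaced a visit-based score with a date-based one. An early Visit 9 scan that shows a heartbeat no longer counts, so the score depends on whether a second, later scan reached the eCRF. The protocol neither schedules that scan nor plainly tells sites to enter one done elsewhere. A woman can then be a failure on the primary endpoint and a live birth from the same transfer in the post-trial analysis, and SAP 9.2 has no rule for that conflict.

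Two consequences matter in a non-inferiority trial. Equal loss of true successes in both arms shrinks a real deficit and makes non-inferiority easier to claim. Unequal loss biases the difference directly. Equal loss cannot be presumed: Protocol 3.3.3 and 5.5 blind the ultrasound staff, embryologists and central laboratory, but do not list the site staff who schedule visits and enter data.

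**Working it through.** **1. Reproduce the design.** Protocol 9.1 gives "The study has at least 80% power, with 275 subjects per treatment group", a "1-sided significance level of 0.025 with a 12% non-inferiority margin", "by assuming an ongoing pregnancy rate of 50% for both treatment groups".

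- n per arm = (1.960 + 0.842)² × (0.5×0.5 + 0.5×0.5) / 0.12² = 272.5, so 273 against 275 stated.
- At 275 per arm, SE = √(0.5/275) = 0.0426. Power = Φ(0.12/0.0426 − 1.960) = 80.4%.
- 275/0.92 = 298.9, so 299 per arm and 598 in total, against about 600 stated.

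The stated design reproduces, and this point does not change it.

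**2. Who is exposed.** The cut-off of 49 with the +1 convention is 48 elapsed days. Eight full weeks is 56 days, so a scan up to 8 days before that already counts. A visit four weeks ahead of 8-9 weeks falls at about 28 to 35 elapsed days (56 − 28 to 63 − 28), well outside. The most extreme cases that the sponsor describes therefore need a later scan.

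**3. Effect on the test.** Let m be the share of true ongoing pregnancies scored as failures. The documents give no value, so m is an assumption. The observed rate is true rate × (1 − m). The error below is the exact probability, from two binomials with 300 per arm, that the SAP's normal-approximation lower limit exceeds −12 points when the true rates are 38% (MENOPUR) and 50% (Gonal-f).

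| m, equal in both arms | Women lost per arm at a 50% rate (300 × 0.5 × m) | Observed rate when truth is 50% | True −12 points appears as | One-sided error |
|---|---|---|---|---|
| 0 | 0 | 50.0% | −12.0 | 2.60% |
| 2% | 3 | 49.0% | −11.8 | 2.95% |
| 5% | 7.5 | 47.5% | −11.4 | 3.55% |
| 10% | 15 | 45.0% | −10.8 | 4.79% |

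Power at equal true rates of 50% stays at about 85% throughout.

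**4. Unequal loss.** At equal true rates of 50%, a 5-point gap in m shifts the difference by 0.50 × 0.05 = 2.5 points, about a fifth of the margin.

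- Gonal-f loses more: error at the margin is 9.2% (0% on MENOPUR, 5% on Gonal-f) or 11.8% (5% and 10%).
- MENOPUR loses 5% and Gonal-f none: power at equal true rates falls from 85% to 66%.

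**The case against.** A reader might infer that the protocol tells sites to keep these scans out of the eCRF, and that live pregnancies are therefore being scored as failures. The documents do not support that.

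- Protocol 6.7 exempts pregnancy data that are new or changed. A later dated heartbeat that settles the endpoint can be read as new.
- The exclusion in Protocol 7.1.3 covers scans done during the ICSI treatment and may not reach scans in pregnancy. The sentence before it says that, in pregnant women, a fetal heartbeat will be collected.
- A mistimed Visit 9 could be repeated in the window. That would be the required assessment, and Protocol 3.3.7 allows unscheduled visits.
- Neither the number scanned early, nor the number without a later scan, nor the split by arm is given. At m = 2% the error barely moves, and nothing shows that m reaches 10% or differs between arms.
- A loss before the window is a failure whether or not it is entered, so the readier recording of losses does not itself change a score.
- Dilution under equal loss follows from any rule that treats missing as failure, and Protocol 9.6.2 prespecified that rule.

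All of this stands. It turns a claim of barred data into one of unsecured data. It does not supply a requirement to enter the later scan, and it does not resolve the four wordings of the rescue.

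**Conclusion.** The point holds as a possibility that the plan leaves open, not as a demonstrated misclassification. Under SAP 9.2 as written, a woman with an early heartbeat scan and no later one on record is a primary failure even if the same pregnancy ends in a recorded live birth. Early visits did occur, and capture of the later scan rests on site interpretation.

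The size is unknown. With equal loss of 2% to 10% the error inflation is modest (2.6% to between 3.0% and 4.8%), and the reported rate is understated by 1 to 5 points at a true 50%. The larger risk is imbalance, at 2.5 points of bias for a 5-point gap in loss. These figures rest on assumed loss shares, 300 women per arm, a 50% Gonal-f rate and, for the error figures, a true difference exactly at the margin.

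**What to change.** 1. **Query before database lock, blind to arm.** For every mITT subject whose last recorded heartbeat scan is earlier than day 49, ask the site to check source records for any heartbeat scan at or after day 49, and enter its date and result.
2. **Use one rescue definition** in SAP 9.1.3, 9.2, section 12 and the change log, stating which evidence counts and from which day.
3. **Report by arm** the number of early-scanned women with no later scan. Add a supportive primary analysis that counts a documented delivery from the fresh transfer, or a loss dated after 11 weeks, as ongoing pregnancy. If delivery data arrive after the primary analysis, give it as a supplement. State its limit: Protocol 6.9 requires delivery data only where ongoing pregnancy was confirmed, so coverage depends on how sites classified the early visit.

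Rewriting Protocol 6.7 and 7.1.3 would probably come too late, since the synopsis planned the last visit for December 2016 and SAP v4.0 is dated March 2017. The cost is one round of site queries, some chart retrieval and a few SAP sentences. No new visits or patients are needed.
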